#### 6.1 Informed consent and inclusion

Informed consent (i.e. informed consent signed and dated) is provided. Subjects who meet all other inclusion/exclusion criteria, were considered to be enrolled in this study.

#### 6.2 Subject identification number

Each subject is given a unique identification number, subject numbering rules are sample type number + sequence number, sequence number. The value starts from 001 and increases in sequence, for example, NFC001. All study documents (such as case reports, clinical records, etc.) will adopt this identification number

#### 6.3 Data source/Data collection process

Data for this study were obtained by extracting routine clinical records of enrolled subjects. The investigator was asked to stay throughout the monitoring period enter information from the original medical record into the study record sheet.

#### 6.4 Data Collection Procedure

- (1) Record demographic data: date of birth, gender, initials;
- (2) Medical history and physical examination (including vital signs, height, weight, BMI, physical examination of all systems; HCC history Present history, etiology)
- (3) Clinical presentation (symptoms, tumor location, stage of diagnosis), treatment modalities (surgical intervention, adjuvant therapy) and survival outcome (survival time, recurrence), details of surgical procedure (resection extent, lymph node dissection);
- (4) Record laboratory test results: including preoperative laboratory values (such as CEA, CA19-9 levels) and available genetic markers Markers (KRAS mutation, dMMR/MSI-H);
- (5) Pathological findings (tumor differentiation, lymphatic vascular infiltration, perineural infiltration) were recorded.

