Statistic analysis	
Statistical analysis
 
Rigorous statistical methods were used to analyze the collected data. Survival outcomes, including OS and DFS, were calculated from the date of diagnosis until the date of death or last follow-up, and from the date of diagnosis until the date of disease recurrence or last follow-up of DFS. Kaplan-Meier survival curves were generated to illustrate survival trends over time, and log-rank tests were used to compare the distribution of survival among different patient subgroups. Cox proportional hazard models were used to identify independent prognostic factors affecting survival. Variables considered in the model included demographic factors (age, sex), clinical features (BMI, jaundice, bleeding, anemia), preoperative laboratory values, treatment details (radical resection, adjuvant therapy), and pathological findings (AJCC stage, tumor differentiation and lymph node involvement rate). Hazard ratios (HRs) and 95% confidence intervals (CI) were calculated to estimate the strength of the association between each variable and survival outcomes.

Follow-up visit	The patients included in this study were from a hospital cohort that included cases diagnosed and treated in the Department of General Surgery at Nanfang Hospital of Southern Medical University. Inclusion criteria were histologically confirmed non-ampulla DA, including all stages of disease at diagnosis. Patients were excluded if they had ampulla cancer or other forms of gastrointestinal cancer, had incomplete medical records, or lost follow-up shortly after diagnosis.
Statistical approach	Statistical methods SPSS 25.0 and Prism 8.0.1 software were used for all statistical analyses.
Expected progress	Expected progress: From April 2024 to May 2024, data collection, sorting and analysis will be completed. From May 2024 to June 2024, monograph writing, submission and conclusion will be completed

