The treatment of DA faces several challenges, including the lack of established guidelines based on worldwide scientific evidence, the difficulty of early detection due to the rarity of the disease and the lack of specific screening markers, and the limited evidence supporting various treatment modalities. Surgical resection is the only possible treatment for DA. The complexity of surgery, which often includes pancreaticoduodenectomy, has evolved over the years, and advances in perioperative care and surgical techniques have helped reduce morbidity and mortality, but there has been no uniform improvement in long-term survival outcomes. Adjuvant therapy, including chemotherapy and radiotherapy, has been explored as a means of improving survival, especially in cases with adverse pathological features, such as lymph node involvement or the advanced stage of diagnosis. Despite these reasons, the efficacy of adjuvant therapy for DA remains controversial. There have been no randomized controlled trials comparing the efficacy of single surgery with perioperative adjuvant treatment for DA. All of the studies were retrospective comparisons of the outcomes of surgery alone and combined surgery, so there may be selection bias in patients. Numerous meta-analyses and systematic reviews have investigated the treatment of DA in depth, but most studies have been retrospective, single-center, and small-sample size series, especially in China. To address this knowledge gap, we conducted a hospital-based cohort study designed to investigate long-

term outcomes in patients with DA and to disaggregate the effects of tumor characteristics, surgery, and adjuvant therapy on survival outcomes.

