## **2. Study purpose**

2.1 Main Objectives: Whether radical DA resection is associated with improvement in 5-year overall survival

2.2 Secondary objectives: Adjuvant therapy, pancreatic invasion, and advanced tumor stage were identified as significant predictors of overall survival

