## **4. Study design**

This retrospective analysis was designed to clarify long-term survival outcomes in patients diagnosed with non-ampulla DA. The study spans a 15-year period, from 2009 to 2023, capturing a comprehensive dataset that reflects advancements in diagnostic and treatment strategies over time. This cohort of 400 patients was carefully selected to provide a robust data set for analyzing survival outcomes and identifying prognostic factors affecting overall survival (OS) and disease-free survival (DFS).

No randomized or any protocol-driven treatment will be administered or provided to the subjects during the study. If clinically applicable, treatment decisions and treatment options are made at the discretion of the treating physician.

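### Postoperative complications are neither collected nor modelled, so if they reduce adjuvant receipt and worsen survival, their effect on the adjuvant hazard ratio cannot be removed

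*Combined protocol and SAP*

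**What the plan says.** Section 6.4, item (3), lists presentation, treatment modalities, survival outcome and "details of surgical procedure (resection extent, lymph node dissection". No item in 6.4 names complications, reoperation or length of stay. Laboratory items are described as "including preoperative laboratory values (such as CEA, CA19-9 levels", so no postoperative value is named either.

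The Cox covariates appear in the statistical analysis row of the Summary of research scheme. Besides age, sex and preoperative laboratory values, they are "clinical features (BMI, jaundice, bleeding, anemia" and "treatment details (radical resection, adjuvant therapy), and pathological findings (AJCC stage, tumor differentiation and lymph node involvement rate". None describes recovery from surgery.

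Section 2 gives the secondary objective as "Adjuvant therapy, pancreatic invasion, and advanced tumor stage were identified as significant predictors of overall survival", and section 3 makes overall survival with adjuvant therapy a secondary endpoint. Section 4 says that "treatment decisions and treatment options are made at the discretion of the treating physician". Surgical morbidity appears once, in section 1, where "advances in perioperative care and surgical techniques have helped reduce morbidity and mortality".

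**The concern.** A complication falls between the operation and the decision on adjuvant therapy. Suppose it makes adjuvant therapy less likely and also shortens survival. It is then a confounder of the adjuvant comparison, and the group without adjuvant therapy contains more patients with a difficult recovery. Their worse survival would count in favour of adjuvant therapy even if the therapy did nothing. The listed covariates are tumour features or preoperative patient features, so at best they stand in for a postoperative event indirectly.

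Section 1 criticises earlier comparisons of surgery alone with combined treatment as retrospective and open to selection. This study makes the same kind of comparison and does not collect one plausible source of that selection. Unlike a covariate that is merely left out of the model, this one cannot be added at the analysis stage unless someone returns to the charts.

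**Working it through.** The documents give no complication rate, adjuvant rate, event count or effect size, and the sample size of 400 has no derivation. There is therefore no planned figure to reproduce. Every rate below is an assumption, and the true adjuvant hazard ratio is set to 1.0 throughout.

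**Formula.** Let p1 and p0 be the share with a major complication among patients with and without adjuvant therapy, and h the hazard ratio of a complication for death. To first order:

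apparent HR = (1 + p1(h - 1)) / (1 + p0(h - 1))

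**Complication shares assumed directly**
- 15% vs 30%, h = 1.5: 1.075 / 1.150 = 0.935
- 15% vs 30%, h = 1.8: 1.120 / 1.240 = 0.903
- 10% vs 35%, h = 2.0: 1.100 / 1.350 = 0.815

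Simulated Cox models with 40,000 patients gave 0.94, 0.91 and 0.86. Reruns under other assumed baseline hazards gave 0.91-0.96, 0.90-0.95 and 0.84-0.87.

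**Shares derived from receipt.** Take 30% with complications and h = 1.6.
- Receipt 40% with and 60% without a complication: p1 = 0.12/0.54 = 0.222, p0 = 0.18/0.46 = 0.391, apparent HR = 1.133/1.235 = 0.918.
- Receipt 30% vs 60%: p1 = 0.09/0.51 = 0.176, p0 = 0.21/0.49 = 0.429, apparent HR = 1.106/1.257 = 0.880.

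**Range, for 20-40% with complications**

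| Receipt with vs without complication | h | Apparent HR | False-positive rate, 160 deaths assumed |
|---|---|---|---|
| 50% vs 50% | any | 1.00 | 5% |
| 45% vs 55% | 1.3-2.0 | 0.93-0.98 | 5-7% |
| 40% vs 60% | 1.3-1.6 | 0.91-0.96 | 6-9% |
| 40% vs 60% | 2.0 | 0.87-0.90 | 10-14% |
| 30% vs 60% | 1.3-1.6 | 0.87-0.95 | 6-14% |
| 30% vs 60% | 2.0 | 0.81-0.85 | 17-26% |
| 60% vs 50% | 1.3-2.0 | 1.02-1.07 | 5-7% |

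The last column uses a two-sided 5% test and variance 1/(deaths × a × (1 - a)) for the log hazard ratio, with a the share given adjuvant therapy. For 160 deaths and a = 0.5 the standard error is √(1/40) = 0.158. An apparent HR of 0.94 is then about 0.4 of a standard error from 1, and 0.91 about 0.6.

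**Effect of adjusting.** Simulated Cox models (400 replicates; 250 or 400 patients; 30% with complications; h = 1.6) gave 0.92-0.93 for receipt 40% vs 60% and 0.89-0.90 for 30% vs 60%, the latter with about 13% false positives. With the complication term added, the hazard ratio was 1.00 in each case and the rejection rate 3-6%, which is nominal within simulation error.

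**Opposing component.** Add one unmodelled adverse-pathology factor: prevalence 40%, hazard ratio 1.8, odds of adjuvant receipt multiplied by 2 if present and divided by 1.4 if absent, starting from 50% receipt. Receipt becomes 66.7% and 41.7%. The factor is then present in 0.267/0.517 = 0.516 of patients with adjuvant therapy and 0.133/0.483 = 0.276 of those without. Its own bias is (1 + 0.516 × 0.8)/(1 + 0.276 × 0.8) = 1.413/1.221 = 1.157. Combined with the complication component:
- 1.157 × 0.918 = 1.06
- 1.157 × 0.880 = 1.02

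Simulation gave 1.06 and 1.02. Adjusting for complication alone then left about 1.15, so the two adjustments belong together.

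**Landmark.** With the complication effect confined to the first 0.5 year and a 0.5-year landmark, the simulated adjuvant hazard ratio was 0.97-1.03.

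**The case against.** The strongest reply is that the documents supply neither link the argument needs. They do not say that complications affected who received adjuvant therapy, or that complications shortened survival. The only driver of adjuvant use they mention, in section 1, is adverse pathology or advanced stage, which works in the opposite direction. A reader might infer that the planned adjuvant hazard ratio is biased towards benefit. The documents do not support that as a net statement: stage, nodes and differentiation are in the model, but lymphovascular and perineural invasion are collected and not named there, and the check shows that one such factor can reverse the sign. This stands.

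A reader might also infer that a landmark analysis would be no help. That holds only if the excess hazard lasts beyond the landmark. A landmark removes the part due to early deaths.

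The size is modest unless selection is strong, and other weaknesses in the same estimate come first: survival is counted from diagnosis, and patients of all stages enter, so unresected patients may sit in the comparison. This also stands, and it limits the priority of the point.

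Finally, the covariate list may be open-ended, and the records could still be searched. This is weak, because nothing commits the study to extracting complications.

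**Conclusion.** The omission is plain in the text, and it affects a stated secondary objective. The direction of the resulting bias is conditional. If complications lower adjuvant receipt and worsen survival, this component moves a true hazard ratio of 1.0 to about 0.91-0.96 under moderate assumptions (for example, receipt 40% vs 60% and a complication hazard ratio of 1.3-1.6). It moves it to about 0.81-0.87 under strong selection (for example, receipt 30% vs 60% or shares of 10% vs 35%, with a complication hazard ratio near 2.0). If either link is absent, this component is nil. The net bias of the planned estimate could lie on either side of 1. This is a cheap improvement, ranking below the time-origin and population problems.

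**What to change.** Add three items to section 6.4(3): major postoperative complication (yes/no or grade, with date), reoperation, and date of discharge after the index operation. The complication date helps to confirm that the event came before the adjuvant decision.

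Specify a separate Cox model for adjuvant therapy in resected patients only; the plan has no such model, and the adjustment works only there. Include major complication alongside stage, nodes, differentiation, and the already collected lymphovascular and perineural invasion. Leave complication out of the model for the resection effect, where it lies on the causal path from surgery to survival.

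The cost is a few items from the routine records that section 6.3 already uses, and a few more model terms. It is best settled before extraction, since the records span 2009 to 2023 and a second pass would cost more. Complications may be less well documented in the earliest years, so the plan should report how many values are missing and how they are handled. The change does not address the start of survival time at diagnosis, which needs its own solution, such as a landmark or time-dependent analysis.

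### Lymphovascular and perineural infiltration are recorded but not listed as Cox covariates, so the adjuvant-therapy hazard ratio may carry residual confounding

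*Combined protocol and SAP*

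**What the plan says.** Section 6.4(5) lists the pathology to be extracted: "Pathological findings (tumor differentiation, lymphatic vascular infiltration, perineural infiltration) were recorded".

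The Cox model is described only in the synopsis (Summary of research scheme, Statistic analysis). Its candidate variables open with "Variables considered in the model included demographic factors (age, sex), clinical features (BMI, jaundice, bleeding, anemia), preoperative laboratory values", continue with "treatment details (radical resection, adjuvant therapy", and end with "pathological findings (AJCC stage, tumor differentiation and lymph node involvement rate". Section 10 covers group comparisons, software and the significance level. It adds no covariates, propensity score or sensitivity analysis.

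Adjuvant therapy appears in the secondary objective (section 2.2) and the secondary endpoint (section 3.2). On how patients came to be treated, section 4 says that "treatment decisions and treatment options are made at the discretion of the treating physician". The background (section 1) says that adjuvant therapy "has been explored as a means of improving survival, especially in cases with adverse pathological features", and gives two examples: "such as lymph node involvement or the advanced stage of diagnosis". It also warns that earlier retrospective comparisons of adjuvant treatment may suffer from selection bias.

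**The concern.** The study compares patients who did and did not receive adjuvant therapy without randomisation. The planned protection against confounding by indication is the covariate list. Two pathology variables that the study will extract anyway are not on it.

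If clinicians gave adjuvant therapy more often when they saw lymphovascular or perineural infiltration, and if these features worsen survival at a given stage, nodal burden and grade, the adjuvant group starts with a poorer prognosis that the model does not see. Along this path the hazard ratio moves upwards, and a real benefit would look smaller than it is. The result at stake is a named secondary objective, in a study whose own background criticises earlier work for this kind of bias.

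**Working it through.** **Step 1: set the lists side by side.**

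| Pathology item | Recorded in 6.4(5) | In the synopsis Cox list |
|---|---|---|
| Tumour differentiation | yes | yes |
| Lymphovascular infiltration | yes | no |
| Perineural infiltration | yes | no |
| AJCC stage | not in item 5 (stage at diagnosis is in item 3) | yes |
| Lymph node involvement rate | not in item 5 (node dissection is in item 3) | yes |

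Two of the three items in 6.4(5) have no counterpart in the model. Both adverse features named in the background, nodal involvement and advanced stage, do have one.

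**Step 2: size of a possible bias.** The plan states no hazard ratio, adjuvant share, prevalence of infiltration or event count, so there is no figure of its own to reproduce. Every input below is an assumption.

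For one omitted binary factor, the adjuvant hazard ratio is multiplied by approximately

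B = [1 + p1(HRu − 1)] / [1 + p0(HRu − 1)],

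where p1 and p0 are its prevalence with and without adjuvant therapy, after accounting for the listed covariates, and HRu is its own mortality hazard ratio. With p0 = 30%:

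| HRu | p1 = 30% | p1 = 40% | p1 = 50% | p1 = 60% |
|---|---|---|---|---|
| 1.3 | 1.00 | 1.03 | 1.06 | 1.08 |
| 1.5 | 1.00 | 1.04 | 1.09 | 1.13 |
| 2.0 | 1.00 | 1.08 | 1.15 | 1.23 |

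The largest entry is (1 + 0.6 × 1.0)/(1 + 0.3 × 1.0) = 1.6/1.3 = 1.23. A true hazard ratio of 0.70 would then appear as 0.70 × 1.23 = 0.86. With a 40% versus 30% imbalance and HRu 1.3 it would appear as 0.72. With no remaining imbalance it stays at 0.70.

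If both factors were omitted and were independent of each other, their multipliers would multiply. At 50% versus 30% this gives 1.055² = 1.11 for HRu 1.3 and 1.154² = 1.33 for HRu 2.0. Independence is a generous assumption for two features of the same tumour.

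**Step 3: can the model carry two more terms?** Assume about 16 parameters now and 18 after the change, in all 400 patients.

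- 40% deaths: 400 × 0.4 = 160 events; 160/16 = 10.0 per parameter, falling to 160/18 = 8.9.
- 70% deaths: 400 × 0.7 = 280 events; 280/16 = 17.5 per parameter, falling to 280/18 = 15.6.

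The resected subset would have fewer events. Even so, the relative loss from two binary terms is small, and sample size is no strong reason to leave them out.

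**The case against.** The strongest reply is that the plan already adjusts for what its background names. Nodal involvement and stage are in the model, and so is differentiation. No section links either infiltration variable to the decision to give adjuvant therapy. This stands, and it limits the point to possible residual confounding.

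A reader might infer something stronger: that the protocol says adjuvant therapy was given mainly to patients with adverse pathology, so that its hazard ratio is confounded and biased towards harm. The documents do not support this. The background sentence describes what has been studied in the literature, not how this cohort was treated. The stage and node examples are introduced as examples, so other features are not ruled out, but neither are these two ruled in. The net direction is also open. Survival is counted from diagnosis while adjuvant therapy starts later, and that works towards apparent benefit.

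Three lesser replies stand in part:

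- **Open list.** The synopsis says the model's variables included those named, so the list may not be complete. If so, the adjustment set is not fixed in advance, which is itself a reason to name the two variables.
- **Precision.** Assuming 200 deaths and 40% adjuvant use, the standard error of the log hazard ratio is 1/√(200 × 0.4 × 0.6) = 0.144, a 95% confidence factor of exp(1.96 × 0.144) = 1.33 either way. Most of the multipliers in the table are well inside that. But a bias within the interval still shifts the estimate and does not shrink with more patients.
- **Missing data.** Section 6.4(4) limits the genetic markers to those available, and 6.4(5) sets no such limit. That does not show that routine reports from 2009 to 2023 always state both features. The fix must allow for gaps.

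Pancreatic invasion, which is named in the secondary objective but absent from the Cox list, is a separate and plainer gap. It does not answer this one.

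**Conclusion.** The point holds in a limited form. It is established from the text that both infiltration variables are to be recorded, that neither is in the only Cox list, that treatment was discretionary, and that the adjuvant association is a secondary objective. The adjuvant hazard ratio may therefore be residually confounded.

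Whether it is depends on imbalance that remains after adjustment for stage, nodes and grade, and the documents say nothing about that. The range of 1.00 to about 1.23 for one omitted factor is an illustration that rests wholly on the assumed prevalences (30% against 30% to 60%) and prognostic hazard ratios (1.3 to 2.0). It is not an estimate for this study. If the features were less common among adjuvant patients after adjustment, the factor would fall below 1.00.

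**What to change.** Add lymphovascular and perineural infiltration to the prespecified covariates of the adjuvant-therapy Cox model, alongside those already listed, and fit that model in resected patients, where surgical pathology exists. If the sponsor prefers to leave them out, the plan should give the reason.

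State a rule for unreported values, for example multiple imputation with a complete-case analysis as a sensitivity check, and report how often each item is missing by adjuvant group. Section 5.3 excludes patients with missing diagnostic or treatment data without saying which items count. The plan should make clear whether an unreported infiltration status is handled by this rule or leads to exclusion.

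This is a cheap improvement but not a free one. Both items are already specified for extraction. The cost is two extra parameters, a smaller analysis set with fewer events for the adjuvant question, and the work of handling incomplete pathology reports.

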### **7. Study termination/suspension criteria**

7.1 The Sponsor has the right to terminate/suspend the study. Before terminating/suspending a clinical study, the sponsor shall notify the investigator, ethics committee and relevant regulatory authorities, and state the reasons. After early termination/suspension of the study, restart of the study must be obtained the Ethics Committee reviewed and agreed.

7.2 Termination/suspension requested by the Ethics Committee.

